4.11 Study Restrictions

4.11.1 Prohibitions and Concomitant Therapy

Prohibited medications and products are detailed in Table 2 (Excluded Medications and Treatments).

Generally, the addition of new medications, including nonprescription medications, during the course of the study is discouraged. However, the short-term use of a medication may be authorized by the Investigator. The Investigator must make the decision to authorize the use of any such a medication only after consideration of the clinical situation, the potential for masking symptoms of a more significant underlying event, and whether the use of the medication will compromise the outcome or validity of the clinical investigation. If medication is required, the name, strength, frequency, duration of use, and reason for use will be recorded in source documents and entered into the CRFs. Medications which have been used chronically by subjects, in particular statins and anti-hypertensives, are allowed for use during the study, except as prohibited in Table 2.

Table 2. Excluded Medications and Treatments

Excluded Medications and Treatments	Washout Period from Baseline (Visit 2)
Topical calcineurin inhibitors, PDE-4 inhibitors (Eucrisa®), topical urea-containing emollients, topical salicylic acid-containing emollients, topical antibiotics, topical low potency corticosteroids, topical mid potency corticosteroids	7 days
Topical high potency corticosteroids	14 days
Systemic antibiotics	14 days
Systemic non-biologic treatments for eczema (e.g., cyclosporine, azathioprine, corticosteroids, methotrexate) 
 • Oral JAK inhibitors will be allowed if stopped for reasons other than safety concerns (28 day washout required) 	28 days or 5 half-lives (whichever is longer)
Biologics including Dupixent®	3 months or 5 half-lives (whichever is longer)
Oral retinoids (alitretinoin/Toctino, acitretinin, isotretinoin)	3 months
Cell-depleting biologics such as rituximab	6 months

Excluded Medications and Treatments	Washout Period from Baseline (Visit 2)
UVB or PUVA phototherapy, tanning booths	28 days
Strong Cytochrome P-450 3A4 inhibitors and strong Cytochrome P-450 3A4 inducers	14 days
All investigational drugs	3 months (biologics); 1 month (oral); 2 weeks (topical) - or 5 half-lives (whichever is longer)

Note:

- Ear drop, eye drop and nasal corticosteroid preparations are allowed.
- Inhaled corticosteroid preparations are allowed if used for a stable condition and at a stable dose for >28 days before Baseline (Visit 2) and are continued at the same dose throughout the study.
- Non-medicated emollients, moisturizers and sunscreens will be allowed as normally used by the subjects. These should not be applied to treatment sites 2 hours before or after investigational product application.
- There is no washout for sedating or nonsedating antihistamines. During the study, systemic treatment with sedating antihistamines is prohibited. During the study, systemic treatment with nonsedating antihistamines in a nonstable regimen is prohibited, while systemic treatment with sedating or nonsedating antihistamines in a stable regimen is allowed.
- Live vaccine therapy is not allowed less than 4 weeks prior to Baseline (Visit 2).

4.12 Treatment

4.12.1 Investigational Product Supplies, Packaging and Labeling

Phase 1 (Cohort 1)

ARQ-252 cream 0.3% will be in 12-gram tubes. The tubes will be labeled in an open-label manner. The tubes dispensed to a subject will be labeled with a unique number.

Phase 2b (Cohort 2)

ARQ-252 cream 0.1%, ARQ-252 cream 0.3% or vehicle formulation will be in 12-gram tubes. The tubes will be packaged in kits, containing 2 tubes of investigational product. The number of kits dispensed to a subject will be based on the dosing frequency, either BID (twice daily) or QD (once daily). The kits and tubes will be labeled with a unique number, in a blinded manner.

Phase 1 and 2b (Cohorts 1 and 2)

The Sponsor will supply sufficient quantities of the investigational product to each site to allow for completion of this study.

Records will be made of the receipt and dispensing of the investigational product supplied. At the conclusion of the study, any unused investigational product will be returned to the Sponsor or designee, or destroyed, as per Sponsor instructions.

Refer to the most current version of the IP Handling Plan for details on accountability, storage, and management of IP.

4.12.2 Treatment Administration

Initial treatment with the IP will occur on Day 1. At the Baseline visit the study staff will demonstrate to the subject how to apply IP using the first tube that is assigned to the subject at enrollment/randomization. Study site staff will demonstrate how two unit doses (two pea size amounts of IP will cover approximately 4% BSA, i.e., both hands entirely) are properly squeezed from the tube and applied as a thin film to cover both hands. IP will be applied to the front and back of both hands, interlacing fingers, rubbing in thoroughly but gently, until the cream has absorbed. The subject will then practice squeezing a similar amount and applying IP. The study staff will confirm that the subject's application technique is correct.

Subjects in Cohort 1 will be instructed to apply IP once daily (QD). Subjects in Cohort 2 will be instructed to apply IP either once daily (QD) or twice daily (BID), as determined at randomization.

IP tubes must be returned by subjects at each study visit, both empty and full, and will be weighed. Re-training will be conducted at subsequent visits as needed (i.e., if the returned tube weighs substantially different than the expected weight).

Subjects will be instructed to refrain from handwashing for 4 hours after IP application, if possible. Subjects may use hand sanitizer within 4 hours of IP application, if necessary. Hand washing and use of hand sanitizer within 4 hours of IP application will be recorded in the subjects' diary and CRF.

4.12.3 Treatment Compliance

Each IP tube will be weighed prior to dispensing at the Baseline visit and at each follow-up clinic visit according to the Schedule of Visits and Assessments ([Section 1.3](#)). When IP is applied in the clinic, the IP tube will be weighed before and after IP application. If the subject's actual use is substantially different than the expected use (see IP Handling Plan), the subject will be retrained on the investigational product application technique.

Subjects will complete a daily diary recording the date and time of each dose applied, any missed doses, and a comment section should the subjects have a comment, e.g., record potential AEs, handwashing or use of hand sanitizer within 4 hours. Site personnel will review the diaries and use the information to question the subject regarding compliance and AEs and then record appropriate information in source documents and complete CRFs. If a subject misses a dose, they should be instructed to return to the protocol investigational product administration schedule (i.e., if subject forgets a dose they should wait until the next planned application and apply as usual).

A subject will be considered compliant with the dosing regimen if the subject applies at least 80% of the expected applications during the investigational product application period and does not miss more than 3 consecutive doses.

Compliance will be assessed by review of the dosing diary. Weight of investigational product applied will be measured for reporting purposes.

If the diary shows less than 80% of expected use, the subject is using too little investigational product and retraining must be conducted and documented.

Compliance will be documented in source and in CRF.

5. STUDY PROCEDURES

5.1 Safety Assessments

The Schedule of Visits and Assessments ([Section 1.3](#)) summarizes the clinical procedures to be performed at each visit. Individual clinical procedures are described in detail below. Additional evaluations/testing may be deemed necessary by the PI and/or the Sponsor for reasons related to subject safety.

This study assesses the safety, efficacy, and PK of ARQ-252 cream 0.1%, ARQ-252 cream 0.3% and vehicle cream. Safety will be determined by evaluating physical examinations, 12-lead ECGs, vital signs/weight, clinical laboratory parameters, local tolerability assessments, and AEs as outlined in the Schedule of Visits and Assessments ([Section 1.3](#)). If deemed necessary, additional safety assessments will be performed at the discretion of the Investigator.

5.1.1 Screening

Before a subject's participation in the clinical study, the Investigator is responsible for obtaining written informed consent from the subject after adequate explanation of the study design, anticipated benefits, and the potential risks. A subject is considered a participant of the trial once the ICF is completely signed.

The following procedures/assessments will be performed at the Screening Visit (within 4 weeks after signing the informed consent):

- Review of medical and surgical history, including any history of allergies and/or contact dermatitis
- Review of childbearing potential (subject or partner of male subject) and contraceptive use (see [Section 5.1.2](#))
- Collection of demographic data including sex, age, race, ethnicity
- Vital signs including temperature, heart rate, and blood pressure
- Chronic Hand Eczema assessments (BSA, IGA, HECSI).
- Limited physical examination of skin, lungs, and heart
- ECG

- Laboratory tests: hematology, chemistry, urinalysis, TSH, T4, serum pregnancy test (for female subjects of childbearing potential), FSH (if indicated to confirm post-menopausal status)
- Completion of WI-NRS and NRS Pain. Subjects in Cohort 2 will also complete the QOLHEQ.
- Collection of concomitant medications and adverse events

Medical history of chronic hand eczema will include the following information, which will be recorded in the CRF:

- Morphologic subtype of HE
- Whether the subject has ever been patch tested and if so, the patch test results and any positives (e.g., nickel).
- Distribution on hands (palmar vs dorsal vs interdigital vs pulpitis)

All screened subjects will receive a screening number at the time of informed consent. Subjects in Cohort 2 will be entered into the IRT system at the time of consent.

Subjects may be re-screened one time, the original assigned Subject ID screening number will be used for re-screening.

[figure not shown]
5.1.2 Contraception Requirements

Previous nonclinical research showed that the active ingredient in ARQ-252 can harm fetal development. Subjects engaging sexual intercourse that could lead to pregnancy must adhere to the following pregnancy testing and/or contraception requirements.

Female Subjects

Female subjects of childbearing potential (FOCBP) must have a negative serum pregnancy test at Screening and negative urine pregnancy test at Baseline (Visit 2). For FOCBP involved in any sexual intercourse that could lead to pregnancy: the subject must agree to use a highly effective contraceptive method for at least 4 weeks prior to Day 1. Additionally, from Day 1 until at least 4 weeks after the last investigational product administration, these subjects must agree to use at least 1 highly effective contraceptive method in addition to 1 barrier method of contraception. The acceptable methods of contraception are listed below in the [Figure 1](#).

Figure 1. Contraception Requirements for Female Subjects

¹Subjects using hormonal contraceptives must have been on a stable dose for at least 4 weeks before Day 1.

²The above list of contraceptive methods does not apply to subjects who are abstinent for at least 4 weeks before Day 1 and will continue to be abstinent from penile-vaginal intercourse throughout the study. The reliability of sexual abstinence needs to be evaluated in relation to the duration of the clinical trial and the preferred and usual lifestyle of the participant.

³Female condom and male condom should not be used together.

Male Subjects:

Males, if engaging in sexual intercourse with a female who is pregnant or a female of childbearing potential, must agree to use a condom every time during the study and every time subsequently until 4 weeks after the last investigational product administration.

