
Study Population:
	
For both Cohorts, subjects will be male and female adults (≥ 18 years of age), with chronic hand eczema, and an Investigator's Global Assessment (IGA) of disease severity of at least Mild ('2') at Baseline. In Cohort 2, subjects with IGA of 'Mild' will be limited to 20% of total enrollment, and subjects with IGA of 'Severe' will also be limited to 20% of total enrollment.
 
 • Cohort 1 will include approximately 6 evaluable subjects, assigned to ARQ-252 cream 0.3% QD • Cohort 2 will include approximately 215 subjects, randomized 2:2:1:1:1 to ARQ-252 cream 0.3% QD : ARQ-252 cream 0.3% BID : ARQ-252 cream 0.1% QD : vehicle cream BID: vehicle cream QD

Duration of Participation for Subjects:
	
Cohort 1: Screening (up to 4 weeks), Treatment phase (2 weeks), and follow-up (1 week post-treatment completion) for a total of 7 weeks
 
Cohort 2: Screening (up to 4 weeks), Treatment phase (12 weeks), and follow-up (1 week post-treatment completion); for a total of 17 weeks

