4.7 Selection of Study Population

4.7.1 Inclusion Criteria

Subjects must fulfill all of the following inclusion criteria to be eligible for participation in the study:

1. Participants legally competent to sign and give informed consent.
2. Males and females 18 years of age and older (inclusive) at the time of consent.
3. Clinical diagnosis of chronic hand eczema, defined as hand eczema persistent for more than 3 months, or returned twice or more within the last 12 months (Diepgen 2009). Generally stable disease for 6 weeks. Both irritant and non-irritant etiologic forms are allowed. All morphologic types are allowed, e.g., vesicular/dyshidrotic, hyperkeratotic, nummular, and other types.
4. An Investigator's Global Assessment of disease severity (IGA) of at least Mild ('2') at Baseline (Visit 2). (In Cohort 2, subjects with IGA of 'Mild' will be limited to 20% of total enrollment, and subjects with IGA of 'Severe' subjects will also be limited to 20% of total enrollment).
5. Chronic hand eczema involving at least 0.3% body surface area total (i.e., approximately a third of one handprint) lesions on both hands added together at Baseline (Visit 2).
6. Female subjects of childbearing potential (FOCBP) must have a negative serum pregnancy test at Screening and negative urine pregnancy test at Baseline (Visit 2). For FOCBP involved in any sexual intercourse that could lead to pregnancy: the subject must agree to use a highly effective contraceptive method for at least 4 weeks prior to Day 1. Additionally, from Day 1 until at least 4 weeks after the last investigational product administration, these subjects must agree to use at least 1 highly effective contraceptive method in addition to 1 barrier method according to Contraception Requirements (Figure 1).
7. Females of non-childbearing potential must either be post-menopausal with spontaneous amenorrhea for at least 12 months (post-menopausal status will be confirmed with FSH testing) or have undergone surgical sterilization (permanent sterilization methods include hysterectomy, bilateral oophorectomy, hysteroscopic sterilization, or bilateral salpingectomy) according to Contraception Requirements (Figure 1).
8. Males, if engaging in sexual intercourse with a female who is pregnant or a female of childbearing potential, must agree to use a condom every time during the study and every time subsequently until 4 weeks after the last investigational product administration.

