12. Current or a history of cancer within 5 years with the exception of fully treated skin basal cell carcinoma, cutaneous squamous cell carcinoma or carcinoma in situ of the cervix.
13. Subjects that have received live vaccine therapy less than 4 weeks prior to Baseline (Visit 2), immunosuppressive drugs less than 4 weeks prior to Baseline (Visit 2), or have known infection with mycobacterium tuberculosis, hepatitis B or C, or HIV, or have a diagnosis of an immunodeficiency disorder.

14. Subject had a major surgery within 4 weeks prior to Baseline (Visit 2) or has a major surgery planned during the study.
15. Known or suspected:
 - severe renal insufficiency or severe hepatic disorders
 - hypersensitivity to component(s) of the investigational product which include SHR0302, butylated hydroxytoluene (BHT), benzyl alcohol, dimethyl sulfoxide, cyclomethicone, dimethicone (350 cst), ST-Elastomer 10, water, propylene glycol, polyethylene glycol 200, Pemulen TR1, Carbopol 974P, ethylenediaminetetraacetic acid, trolamine and D-limonene.
16. Pregnant or lactating women or women planning to become pregnant during the study and / or within 28 days following the last dose of investigational product.
17. Subjects who cannot discontinue the use of strong systemic Cytochrome P-450 3A4 inducers e.g., efavirenz, nevirapine, glucocorticoids, barbiturates (including phenobarbital), phenytoin, rifampin and carbamazepine for 2 weeks prior to Baseline (Visit 2) and during the study period.
18. Subjects who cannot discontinue the use of strong systemic Cytochrome P-450 3A4 inhibitors e.g., indinavir, nelfinavir, ritonavir, clarithromycin, itraconazole, ketoconazole, fluconazole, nefazodone, saquinavir, suboxone and telithromycin for 2 weeks prior to Baseline (Visit 2) and during the study period.
19. Subjects with any serious medical condition or clinically significant laboratory, ECG, vital signs or physical examination abnormality that would prevent study participation or place the subject at significant risk, as judged by the Investigator.

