5.4 Final Study Visit – End of Study

Phase 1 (Cohort 1)

The approximate final study visit will occur at Week 3 (Day 22).

Phase 2b (Cohort 2):

The approximate final study visit will occur at Week 13 (Day 92).

For both Cohorts, the procedures performed during these visits are as described in the Schedule of Visits and Assessments ([Section 1.3](#)). A 3-day scheduling window is allowed for this visit. Adverse events will be recorded as reported by the subject and followed to resolution (as necessary).

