5.8 Reporting Pregnancy

During the study, all subjects should be instructed to contact the Investigator immediately if they suspect they might be pregnant (e.g., missed or late menstrual period). If pregnancy is confirmed, Investigational Product must be discontinued immediately, the subject should be referred to an obstetrician experienced in reproductive toxicity for evaluation and counseling, and the subject should be followed until conclusion of the pregnancy. Subject may be required to sign a separate informed consent form to obtain pregnancy follow-up information, per local requirements.

The Investigator is responsible for reporting all available pregnancy information on the pregnancy report and submitting to the Medical Monitor within 24 hours of becoming aware of the event, although pregnancy itself is not considered an AE. Follow-up information detailing the outcome of the pregnancy and the health of the newborn should be reported as it becomes available. Any pregnancy resulting in a congenital abnormality or birth defect of the newborn, or neonatal death occurring within 30 days of the birth must be reported as a SAE, regardless of causality. Any infant death that occurs after the 30 day reporting period that the Investigator suspects is related to Investigational Product must also be reported as an SAE.

Partner pregnancies of a male subject will be reported.

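### The abstinence exemption in Figure 1 note 2 ends with the study, nominally 21 days before the 4-week post-dose contraception period

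*Protocol*

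**What the plan says.** Inclusion 6 (Protocol 4.7.1, repeated in 5.1.2) opens with "For FOCBP involved in any sexual intercourse that could lead to pregnancy". It requires those women to use contraception "from Day 1 until at least 4 weeks after the last investigational product administration". Figure 1 lists the acceptable methods. Its note 2 exempts from the list "subjects who are abstinent for at least 4 weeks before Day 1 and will continue to be abstinent from penile-vaginal intercourse throughout the study", and adds that the reliability of abstinence must be judged against the length of the trial and the participant's usual way of life. Note 2 gives no period after the last application.

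Two neighbouring rules do. Exclusion 16 (4.7.2) bars pregnancy planned during the study and, as a further period, "within 28 days following the last dose of investigational product". The male condom rule (5.1.2) applies "every time during the study and every time subsequently until 4 weeks after the last investigational product administration".

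The Synopsis gives Cohort 2 "follow-up (1 week post-treatment completion); for a total of 17 weeks", and Cohort 1 also has one week of follow-up. Section 5.4 says "The approximate final study visit will occur at Week 13 (Day 92"); for Cohort 1 the final visit is Day 22.

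**The concern.** Three rules about the same reproductive risk name an end that runs from the last application. Note 2 alone ends with the study. A site that follows it to the letter can enrol a woman of childbearing potential with no contraceptive method and a promise of abstinence that stops at the final visit, while a contraceptive user at the same site is bound for at least 4 weeks after dosing.

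This matters because section 5.1.2 says the active ingredient can harm fetal development, and section 2.2 reports teratogenicity in rats and fetal malformations in rabbits after oral dosing. The protocol chose a post-dose period for that reason. The note departs from it without explanation, so sites may advise abstinent women differently about the weeks after the last application.

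**Working it through.** **Does the study include the 4 weeks after dosing?** If it did, note 2 would already reach the same end as inclusion 6. The protocol's own wording points the other way. The male rule, "every time during the study and every time subsequently until 4 weeks after the last investigational product administration", names the study first and the 4 weeks as what follows. Exclusion 16 likewise names the study and the 28 days as separate periods. Both phrases would be redundant if the study already contained those weeks.

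**Reproducing the stated participation totals** (Synopsis and section 4.3):
- Cohort 1: 4 weeks screening + 2 treatment + 1 follow-up = 7 weeks, as stated.
- Cohort 2: 4 + 12 + 1 = 17 weeks, as stated.

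**Inputs for the interval** (section 1.3 schedules and section 5.4):
- Cohort 1: last application Day 15, window ±1 day; final visit Day 22, window ±3 days.
- Cohort 2: last scheduled in-clinic application Day 85, window ±7 days; final visit Day 92, window ±3 days. SAP 6.1.7 agrees with Day 85: it expects 85 once-daily or 170 twice-daily applications from a Cohort 2 completer.
- Post-dose period: 4 weeks = 28 days.

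**Nominal interval and shortfall:**
- Cohort 1: 22 − 15 = 7 days. The 28-day period ends on Day 15 + 28 = 43. Shortfall 43 − 22 = 21 days.
- Cohort 2: 92 − 85 = 7 days. The 28-day period ends on Day 85 + 28 = 113. Shortfall 113 − 92 = 21 days.

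**Range with visit windows.** Shortest interval = earliest final visit − latest last application; longest = latest final visit − earliest last application.
- Cohort 1: shortest (22 − 3) − (15 + 1) = 3 days; longest (22 + 3) − (15 − 1) = 11 days. Shortfall 28 − 11 = 17 to 28 − 3 = 25 days.
- Cohort 2: shortest (92 − 3) − (85 + 7) = −3, taken as 0 days; longest (92 + 3) − (85 − 7) = 17 days. Shortfall 28 − 17 = 11 to 28 − 0 = 28 days.

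No on-schedule combination reaches 28 days in either cohort.

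**The case against.** The strongest reply is that the texts can be read together. Note 2 is a figure footnote, not an entry criterion, and it lifts only the list of methods. A woman who resumes intercourse in the 4 weeks after dosing then fits the opening words of inclusion 6 and falls under its requirement. That reading is available, but it does not close the gap: note 2 asks her for no commitment in those weeks, and at most of those dates she has left follow-up.

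A second reply uses section 7.2.1, which defines study completion as the last visit of the last subject. On that meaning the commitment could run past 28 days for early enrollees. It would not do so for the last ones, and it does not fit the male rule.

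Third, the body of Figure 1 and the consent pages are not in the text reviewed. A duration stated in either cannot be ruled out, although note 2 itself is fully legible.

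A reader might also infer three stronger things that the documents do not support:
- *That abstinence is these women's only commitment.* It is not. Exclusion 16 applies to all women, abstinent or not, and bars anyone planning pregnancy in the 28 days. It sets no contraception duty, however, and does not address an unplanned pregnancy.
- *That 21 of 28 days, or 75%, of the period is unprotected.* The arithmetic is right, but the end of a stated commitment is not a loss of protection. Many such women may remain abstinent, and note 2 requires the reliability of abstinence to be judged.
- *That a pregnancy in those weeks would go unreported.* Section 5.8 begins the subject's instruction with "During the study, all subjects should be instructed to contact the Investigator immediately if they suspect they might be pregnant", and the last scheduled pregnancy test is at the final visit. Both facts apply to every woman of childbearing potential, so they do not set abstinent women apart. Section 5.8 also requires the investigator to report all available pregnancy information within 24 hours of learning of it, without limiting that duty to the study period.

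**Conclusion.** The inconsistency is in the current protocol text. The stated abstinence commitment ends nominally 21 days before the 4-week period that inclusion 6 sets, in both cohorts; with visit windows the shortfall is 17 to 25 days in Cohort 1 and 11 to 28 days in Cohort 2.

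This rests on reading the study, for one subject, as ending at her final visit, and on dosing that ends at Day 15 or Day 85. Applications after Day 85 would shorten the Cohort 2 interval; dispensing at Week 12 is possible with the Medical Monitor's approval. Early stopping can move it either way: longer for a woman who stops dosing but stays in the study, shorter for one who leaves at an early termination visit. How many women would use the exemption is not stated, so the size is in days only.

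It is a gap in wording on a matter of subject safety and deserves correction. It changes no endpoint, analysis population, power or significance level.

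**What to change.** Reconcile Figure 1 note 2 with inclusion 6 and exclusion 16 so that the abstinence commitment states its end relative to the last application, as the neighbouring rules do. Which period is right is for the sponsor to decide.

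Separately, and for all women of childbearing potential, the sponsor should check whether the subject's instruction in section 5.8, which is tied to the study, is consistent with the post-dose period. The two end dates need not be the same; that too is the sponsor's choice.

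The cost is a change of wording in the protocol, and in the consent form if its text matches note 2. No visit, test or analysis is added.
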